As described above, the FACT-L v.4 contains four general and one lung cancer symptom-specific subscales. General subscales include: Physical Well-Being (PWB), Social/family Well-Being (SWB), Emotional Well-Being (EWB), and Functional Well-Being (FWB).(49) The Lung Cancer Subscale (LCS) assesses symptoms commonly reported by lung cancer patients (e.g., shortness of breath; loss of weight; tightness in chest). The Trial Outcome Index (TOI) is derived by adding scores on the PWB and FWB subscales to the LCS. Because they contain the most relevant questions about symptoms and physical functioning, the LCS and TOI were selected as the primary focus of this analysis. All FACT-L questions are rated on five-point Likert-type scales ranging from 0 (“not at all”) to 4 (“very much”). Therefore, because the seven-items PWB, FWB, and LCS subscales scores range from 0–28 for each subscale, TOI scores range from 0–84. Higher scores represent better QoL or fewer symptoms. The primary outcome is the change in the score on the TOI from baseline to 12 weeks. We estimated that with 120 patients (Figure 7), the study would have 80% power with a two-sided α of 0.05 to detect a significant between-group difference of 6 points in the change in the TOI score from baseline to 12 weeks, given a pooled standard deviation of 11.54 and change in the reference group score of 53.(50) After accounting for 30% attrition rate, the expected number of enrolled patients is 156 allocated 1:1 between LuCApp and usual care groups. This sample size will also allow the detection with 80% power with a two-sided α of 0.05 of 2-points difference in the LCS subscale, assuming

a pooled standard deviation of 4.15 and change in the reference group score of 19.3 (50) (Figure 8). The clinically meaningful changes on the TOI and LCS subscales of FACT-L were derived from Cella et al.(51)

The FACT-L questionnaire will be administered electronically (via LuCApp) or via paper in the control group at baseline, 12 weeks and 24 weeks, with an understanding that in the routine care setting, lung cancer therapies administration intervals vary between patients.

Figure 7 - Sample size estimation: 5 to 10 -point difference in change in TOI score at 12 weeks

[figure not shown]
[figure not shown]
[figure not shown]

Figure 8 - Sample size estimation: 1 to 5-point difference in change in LCS score at 12 weeks

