Assuming a constant recruitment rate of 6 patients per week (2 patients per centre) the study is planned to recruit consecutively for 26 weeks (Figure 9).

Figure 9 - Planned recruitment process

Randomization

Randomization services will be provided by AdvicePharma via a computer system using randomly permuted blocks and stratified by trial centers and therapy (i.e.

chemotherapy, immunotherapy and biological therapy). Nurses or physicians involved in the study will take care of the enrollment phase. After signature of informed consent, a randomization code will be generated electronically and assigned to the patient. During the informed consent procedure, the team will go carefully through the different aspects of the study design and will present LuCApp as well as the usual care alternative. During this phase the patient will have an opportunity to discuss her level of experience with mobile technology.

The study is nonblinded, in fact it is not possible to blind the participants when this type of intervention and these outcomes are under investigation.

Participants will remain on study until discontinuation of cancer treatment, voluntary withdrawal, study termination or death.

Statistical methods

The baseline differences between the intervention and control groups will be assessed using the chi-square (χ^2) test for binary demographic data and the independent sample t-test for continuous variables. We will summarize graphically and numerically the distributions of symptoms, outcomes as well as covariates.

For the primary quality of life endpoint, two groups t-test will be used to compare changes from baseline in FACT-L in the experimental group and the control group 12 weeks after randomization. A multivariable linear regression model, with change score as the dependent variable, adjusted for covariates will be fitted. The proportion of patients in each arm who experienced improved, unchanged, or worsened scores from baseline will be compared using χ^2 or Fisher's exact test. This analysis will be run for both any change and clinically meaningful changes for specific subscales (51). The analyses will be repeated at 24 weeks after randomization.

For all other questionnaires, changes from baseline in the LuCApp group and the control group at 12 and 24 weeks after randomization will be computed using t-test comparison. The SCNS-SF34, usability and ZBI data results will be summarized graphically and numerically.

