As a secondary analysis, adjusting for possible confounding factors of demographic variables and clustering in centers, the repeated measures multivariate analysis of covariance will be conducted to determine whether LuCApp affects HRQoL and symptoms as measured via EQ-5D-5L, FACT-L and HADS at different time points of

data collection. Additionally, mixed-effects models will be used to analyze the same subject-specific continuous outcomes with incorporation of terms for intervention, time, centers, and any identified covariates.

Analysis of missing data will first determine how common a problem this is and whether it can be assumed to be missing at random or not missing at random. Multiple sensitivity imputation analyses will be conducted, including last observation carried forward, minimum observation values carried forward, average observation values carried forward, and multiple imputation. EQ-5D value will be set to zero if death occurs before 6 months. Survival time will be calculated from the date of enrollment to the date of death or censoring those alive at the last follow-up with the use of the Kaplan–Meier method. A Cox proportional-hazards model will be fitted to assess the effect of LuCApp on survival, with adjustment for demographic characteristics and baseline performance status.

By combining EQ-5D derived utilities and survival quality-adjusted life years (QALY) for participants in both arms will be computed and compared using two group t-tests between LuCApp and standard care arm. A multivariable linear regression model with QALY as dependent variable will be used to adjust for other covariates. Resource consumption and related costs will be calculated and reported for each treatment group and compared by means of parametric and non-parametric tests (52).

Two-sided P values of less than .05 were considered to indicate statistical significance. All statistical analyses will be performed using STATA® 14.2, StataCorp, Texas.

Ethics & Informed Consent

All procedures involved in the study were consistent with generally accepted standards of ethical practice. The protocol is submitted for ethical clearance to the ethical committees at the three sites involved in the RCT (full list of participating centers is available as an attachment).

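### The primary analysis is not fixed: an unadjusted t-test of change comes first, followed by a regression with unnamed covariates, and baseline TOI, centre and therapy have no declared place in the primary model

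*Combined protocol and SAP*

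**What the plan says.** The Sample size section defines the endpoint: "The primary outcome is the change in the score on the TOI from baseline to 12 weeks". It powers the trial at 80%, two-sided alpha 0.05, for a 6-point difference with 120 patients, "given a pooled standard deviation of 11.54 and change in the reference group score of 53".

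Statistical methods opens its treatment of this endpoint with the t-test: "two groups t-test will be used to compare changes from baseline in FACT-L in the experimental group and the control group", at 12 weeks. The next sentence reads: "A multivariable linear regression model, with change score as the dependent variable, adjusted for covariates will be fitted". It gives no covariate list, no selection rule and no ranking of the two analyses.

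The Randomization section uses "randomly permuted blocks and stratified by trial centers and therapy", the therapies being chemotherapy, immunotherapy and biological therapy.

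Centre enters only later in Statistical methods. The repeated-measures model is introduced with "As a secondary analysis, adjusting for possible confounding factors of demographic variables and clustering in centers". The additional mixed-effects models are described with "incorporation of terms for intervention, time, centers, and any identified covariates". Neither model names therapy or baseline TOI as a covariate.

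**The concern.** Two things are at stake.

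- **Discretion.** There are two tests of the same mean difference in change. One has an open covariate list, and neither is declared decisive. The result that is called primary could therefore be picked after the data are known. The plan also tests baseline differences between arms, which leaves room for choosing covariates from those tests, although it does not say they will be used that way.
- **Precision.** Subtracting baseline is not the same as conditioning on it. Unless the regression slope of the week-12 score on baseline is 1, a model with baseline as a covariate has smaller error variance than the change score alone. The stratification factors would normally be in the primary model too, because the design has balanced on them.

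The trial calls itself a feasibility and pilot study. It nevertheless states formal power and a significance threshold, so the primary comparison will be read as a test.

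**Working it through.** **Inputs from the Sample size section.** Difference 6 TOI points; SD 11.54; two-sided alpha 0.05; 120 evaluable, taken as 60 per arm from the 1:1 allocation.

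**Inputs assumed, because the documents do not give them.** Baseline to week-12 correlation r of 0.3, 0.5 and 0.7; equal variance at the two visits; for centre and therapy, a share R² of 2% to 10% of the variance of change.

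**Step 1: reproduce the plan's figure.** The unadjusted two-sample formula gives 59 per arm (118) by the normal approximation. The t-based calculation gives 59.05, rounded up to 60 per arm (120). Power at 60 per arm is 80.6% by noncentral t with 118 df. The stated 120 is therefore the sample size for the unadjusted t-test.

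**Step 2: variance with and without baseline adjustment.** With score SD σ, the variance of change is 2σ²(1 − r) and the residual variance given baseline is σ²(1 − r²). The ratio is (1 + r)/2, that is 0.65, 0.75 and 0.85.

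**Step 3: if 11.54 is the SD of change.** Adjusted SD = 11.54 × √((1 + r)/2). The adjusted model has 113 df: 120 − 7, for intercept, arm, baseline, two for centre and two for therapy. Half-width = t(0.975) × SD × √(2/60).

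| | t-test | r = 0.3 | r = 0.5 | r = 0.7 |
|---|---|---|---|---|
| SD | 11.54 | 9.30 | 9.99 | 10.64 |
| Power at 120 | 80.6% | 93.8% | 90.3% | 86.5% |
| 95% CI half-width (TOI points) | 4.17 | 3.37 | 3.61 | 3.85 |
| Evaluable N for 80% power | 120 | 78 | 90 | 102 |

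**Step 4: if 11.54 is the SD of scores.** This reading is plausible, because a reference-group change of 53 on a 0–84 scale looks like a mean score, but it is not proven. SD of change = 11.54 × √(2(1 − r)); adjusted SD = 11.54 × √(1 − r²).

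| | r = 0.3 | r = 0.5 | r = 0.7 |
|---|---|---|---|
| SD, change / adjusted | 13.65 / 11.01 | 11.54 / 9.99 | 8.94 / 8.24 |
| Power, t-test | 66.5% | 80.6% | 95.4% |
| Power, adjusted | 84.1% | 90.3% | 97.7% |

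**Step 5: cost of estimating the extra terms.** In simulation (4,000 trials, 120 patients, three centres and three therapies with no true effect), the adjusted power in Step 3 became 93.0%, 88.9% and 85.2%, and in Step 4 82.3%, 88.8% and 97.4%. The cost is at most about 2 points. Type I error at r = 0.5 was 5.3% adjusted and 5.4% for the t-test.

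**Step 6: centre and therapy alone.** With SD 11.54 × √(1 − R²) and 114 df, power moves from 80.6% to 81.4%, 82.6% and 84.5% for R² of 2%, 5% and 10%. Leaving the strata out makes the t-test conservative: with perfect balance its true alpha is 2(1 − Φ(1.96/√(1 − R²))), about 0.048, 0.044 and 0.039.

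**Step 7: cost of an unstated choice.** In simulation with no true effect and 60 per arm, reporting the smaller p-value of the t-test and a single baseline-adjusted regression gave a type I error of about 7% to 8% over r = 0.3 to 0.7. Each test alone stayed near 5%. A longer list of possible covariates can only widen the choice.

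**The case against.** The best defence is that the t-test comes first, directly after the primary endpoint is mentioned, and that the stated sample size is the t-test's own. The natural reading is then t-test primary and regression supportive, and one added word would settle the priority. The t-test is also unbiased, if anything conservative, and meets its stated power at 120 evaluable. The trial is a pilot, so maximum efficiency is not essential.

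The size of the gain also depends on an unknown correlation and an undefined SD. It shrinks as r rises: at r = 0.8 under the SD-of-change reading, adjusted power is 84.5% against 80.6%. Under the SD-of-scores reading at r = 0.7, the gain is only about 2 points. Finally, the later repeated-measures models may use the baseline as one of the time points, and they do include centre.

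All of this is fair, and it limits the size of the point. It does not remove it. Position in a paragraph is not a declaration of priority, the regression is planned for the same endpoint without named covariates, and the longitudinal models are not the primary analysis. Even if the t-test is taken as primary, a better estimator is available from data already collected.

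**Conclusion.** The point holds, as an improvement that should be made and not as the repair of an invalid analysis. That the primary analysis is not declared and its covariates are not named follows from the text alone and needs no assumption.

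The efficiency gain does rest on assumptions: equal variances at the two visits and r between 0.3 and 0.7. At 120 evaluable it is about 6 to 13 points of power if 11.54 is the SD of change, and about 2 to 18 points if it is the SD of scores, before the cost of at most about 2 points for estimating the extra terms. Almost all of it comes from baseline TOI. Centre and therapy add little, and belong in the model mainly because randomisation was stratified on them. The sample size need not rise on this account.

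**What to change.** In Statistical methods, replace the two sentences on the primary endpoint with one declared analysis, for example:

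> The primary analysis is a linear regression of change in TOI from baseline to 12 weeks on arm, baseline TOI, centre and therapy (chemotherapy, immunotherapy, biological therapy). The adjusted between-arm difference, with 95% CI and two-sided p-value, is the primary result. The unadjusted t-test is supportive.

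This keeps the change score as the endpoint. With baseline TOI in the model, the treatment effect is identical to that from a regression of week-12 TOI on the same terms. Any further covariates for sensitivity models should be listed before the data are seen.

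Two wording repairs can be made in the same edit: name TOI instead of FACT-L in the primary analysis sentence, and state in the Sample size section whether 11.54 is an SD of scores or of changes.

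The cost is wording and five degrees of freedom (one for baseline, two for the three centres, two for the three therapies). FACT-L at baseline, centre and therapy are already collected, so no patients, visits or data items are added.

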Usual care will consist of standard procedures currently available at participating centers for monitoring and documenting symptoms. These therapeutical procedures are based on the guidelines developed by the National Comprehensive Cancer Network (NCCN) and the Associazione Italiana di Oncologia Medica (AIOM) (20). Symptoms for control arm patients will be discussed and registered during scheduled clinical visits

with the oncologists. Standard-of-care patients will fill out their PROMs following the same schedule identified for LuCApp patients with paper questionnaires during clinic visits, or at home (having received paper questionnaires during the previous visit) or via telephonic interviews with the research team. Patients are usually allowed to contact their relative sites for concerning symptoms that occur between scheduled visits or advised to see the out-of-hour doctor or the emergency department if needed. This option is also recommended for the intervention arm during weekends.

Outcomes

As discussed above, the overarching research question of this study is to explore and pilot the impact of using LuCApp on relevant outcomes in patients with lung cancer. LuCApp has several functionalities and this pilot explores whether these functionalities impact on the patients' health-related quality of lives (HRQoL) and needs in cancer supportive care. It also aims to assess whether it improves the burden on caregivers and the satisfaction with the use of the app. Finally, the cost-effectiveness of LuCApp will be explored, based on the improvement in HRQoL and the resources being used to manage the disease throughout the study period.

A number of outcome measures have been identified to allow the assessment of the above trial objectives. LuCApp will be evaluated in terms of: (1) impact on HRQoL, (2) impact on cancer supportive care needs, (3) impact on the burden for caregivers, (4) resource use, (5) usability and satisfaction with LuCApp. The rationale for selecting these measures and their characteristics are summarized in the next sections.

(1) HRQoL

The impact on HRQoL of using LuCApp will be measured with existing valid and reliable patient-reported outcome measures (PROMs). Their selection was based on the availability of a validated Italian version, for self-report use, that can be administered both on paper and via smartphones or tablets, and commonly used in lung cancer patients.

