The supportive care needs survey, short form (SCNS-SF34) is a needs assessment questionnaire in cancer supportive care measuring the gap between patients' experience and their expectations (34, 35). It consists of 31 items covering four domains: psychological needs, health system and information needs, physical and daily living needs, and patient care and support needs. For each question, patients are asked to provide an indication of their level of need on a 5-point Likert scale (1: not applicable; 2: satisfied; 3: low need; 4: moderate need; 5: high need) (36). It is applicable to research, clinical settings (36) and routine care (37). It is commonly used to identify priorities for action, to assess the adequacy of current practice in order to identify areas for improvement, and as an intervention tool to reduce patients' perceived needs.

The SCNS-SF34 has been translated and culturally validated (38), and more recently validated in a multicenter study led by [name]. Its construct validity and internal reliability have been demonstrated (36). Its administration as pen-and-paper has been successfully psychometrically tested. It has also been adapted for electronic administration (via touchscreen computer), where the data collected was shown to be equivalent to the data collected from the pen-and-paper version (39).

The SCNS-SF34 will be administered at the end of study, to assess whether some of the supportive care needs were fulfilled in the different study arms. There is still not evidence that the SCNC-SF34 is responsive to change over time, however this is currently being tested in an ongoing longitudinal study assessing how perceived needs change over time over the course of the cancer journey (newly diagnosed cancer patients are being administered the survey four times over the first five years after diagnosis) (36).

(3) Burden on caregivers

The Zarit Burden Interview (ZBI) is a 22-item self-administered scale measuring caregiver burden in health, psychological well-being, finances, social life, and relationship with patient. Each item is measured on a 5-point Likert scale (0=never to 4=nearly always). The total burden is obtained by adding the scores across all 22 items: the higher the score, the higher the burden. Shorter versions have been developed with 18 and 12 items.

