The ZBI was selected on the basis that it has been used in cancer patients (40) and is one of the most widely referenced scales in studies measuring caregiver burden (41). The ZBI was developed for nervous system disorders and mental disorders, but has also been applied to cancer patients (42-45). In one study, the authors explore if caregiver burden was in agreement with patient ratings. Patients had different forms of advanced cancer and their carer's Zarit scores were relatively low. They conclude that Zarit may not capture some important aspects of burden in cancer, given that it was initially developed for dementia patients (42). A second study used the ZBI to assess the impact of breathlessness in lung cancer patients on their caregivers, and found high levels of unmet needs and burden particularly in the more severe cases (43).

Assessment timing of the ZBI will be at the end of the study, and will be administered in paper format. Its criterion validity, construct validity and internal consistency have been demonstrated (40). The Italian version of the questionnaire is valid, reliable and useful for use in clinical contexts and in future studies (46).

(4) Usability and satisfaction of LuCApp

At the end of the study, patients in the intervention arm will have an opportunity to provide feedback on strengths and shortcomings of the application, including unintended/unexpected effects. This session will be of interest also for those who did not use the application as intended by the developers. Use and adoption metrics are important process outcomes to understand the mechanism of action of such intervention. The mHealth application contains a tracking system. Frequency and duration of logins and the activity will be recorded and evaluated. To test user satisfaction with the App, a modified computer system usability questionnaire (CSUQ) will be utilized at the end of the study and will be administered to both patients and clinicians using LuCApp. The CSUQ is an overall satisfaction questionnaire that was developed together with other subjective usability measures at IBM in the nineties (47). The CSUQ is identical to the Post-Study System Usability Questionnaire (PSSUQ),

[figure not shown]

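### No between-arm estimate is prespecified for supportive care needs (SCNS-SF34) or caregiver burden (ZBI), although the protocol asks whether LuCApp affects both

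*Combined protocol and SAP*

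**What the plan says.** The Outcomes section of the combined protocol and SAP poses both questions in comparative terms. On needs: "this pilot explores whether these functionalities impact on the patients' health-related quality of lives (HRQoL) and needs in cancer supportive care". On caregivers: "It also aims to assess whether it improves the burden on caregivers and the satisfaction with the use of the app". Its list of five evaluation domains includes "2) impact on cancer supportive care needs, (3) impact on the burden for caregivers".

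Under (2) Cancer supportive care needs, the SCNS-SF34 is given once, at end of study, "to assess whether some of the supportive care needs were fulfilled in the different study arms". Under (3) Burden on caregivers: "Assessment timing of the ZBI will be at the end of the study, and will be administered in paper format". No baseline is scheduled for either scale.

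The analysis in Statistical methods is "The SCNS-SF34, usability and ZBI data results will be summarized graphically and numerically". The sentence before it reads "For all other questionnaires, changes from baseline in the LuCApp group and the control group at 12 and 24 weeks after randomization will be computed", by t-test. The repeated-measures and mixed-effects analyses are confined to EQ-5D-5L, FACT-L and HADS. QALYs, costs and survival each get a stated comparison of the arms.

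**The concern.** The objectives ask for a comparison of LuCApp with usual care, and the analysis offers description. The analysis sentence also groups two comparative outcomes with usability, which is collected only from people who used the app. Description is right for usability because there is no control arm to compare. It does not answer a question about impact against usual care.

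Without a prespecified contrast, a reader will compare two arm summaries by eye, and may read a chance difference as an effect or a wide interval as no effect. Alternatively, the team will choose a comparison after seeing the data of an unblinded trial. Neither affects the primary outcome (TOI change at 12 weeks), but both weaken what can be said about two of the five outcome domains.

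**Working it through.** **1. Could another part of the plan supply the estimate?**

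- The t-tests for all other questionnaires use change from baseline at 12 and 24 weeks. SCNS-SF34 and ZBI have neither a baseline nor a 12-week value, so no change score exists, and the next sentence treats them separately.
- The secondary models name EQ-5D-5L, FACT-L and HADS only.
- The missing-data paragraph is general. Its carry-forward methods need an earlier value, which a scale measured once does not have.
- The analysis sentence does not say that the summary is by arm. The phrase on study arms under (2) implies it for the SCNS-SF34 only.

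No between-arm difference, interval, test or model is therefore specified for either scale.

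**2. The plan's own sample size.** Inputs from Sample size: difference 6, SD 11.54, two-sided alpha 0.05, power 80%.

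n per arm = 2 × (1.960 + 0.842)² × (11.54/6)² = 2 × 7.85 × 3.70 ≈ 58.1, rounded up to 59 (118 in total).

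The t-test version needs 59.05 per arm, rounded up to 60, or 120 in total. The stated 120 is reproduced. It refers to the TOI at 12 weeks; the plan gives no figure for SCNS-SF34 or ZBI.

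**3. Precision of an end-of-study contrast.** The half-width of the 95% CI in SD units is t(0.975, 2n − 2) × √(2/n).

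| Evaluable per arm | Basis | Half-width |
|---|---|---|
| 60 | the plan's 120 | 1.980 × 0.1826 = 0.36 SD |
| 54.5 | 156 × 0.70 = 109 in total | 1.982 × 0.1916 = 0.38 SD |
| 40 | assumed: heavier loss by end of study, or no caregiver | 1.991 × 0.2236 = 0.45 SD |

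These are for an unadjusted two-arm comparison.

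**4. In points, for ZBI only.** The scale has 22 items scored 0 to 4, so it runs from 0 to 88. The documents give no SD. With an assumed SD of 12 to 16:

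- 60 per arm: 0.3615 × 12 = 4.3 and 0.3615 × 16 = 5.8 points;
- 40 per arm: 0.4452 × 12 = 5.3 and 0.4452 × 16 = 7.1 points.

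No SD is assumed for the SCNS-SF34, so its precision stays in SD units.

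**5. Number of contrasts.** The SCNS-SF34 has four domains; with the ZBI total that makes five models. If the five were independent and LuCApp had no effect, the chance that at least one 95% interval excludes zero would be 1 − 0.95⁵ = 0.23. The domains are likely to be correlated, so this is only a guide, but it is a reason to make no significance claims.

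**The case against.** The strongest reply is that this is a feasibility trial, described as a pilot in Outcomes and in the Discussion, and that description of non-primary scales measured once is a defensible choice. The authors also record limits of both instruments: responsiveness of the SCNS-SF34 to change is not yet shown, and one cited study concluded that the ZBI may miss aspects of burden in cancer. This supports avoiding formal tests. It does not explain why HADS, EQ-5D-5L, QALYs, costs and survival are compared between arms while these two outcomes are not.

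Three further points stand and limit the claim.

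- A reader might infer that the plan rules out any effect estimate or measure of uncertainty. It does not. A numerical summary may contain SDs or intervals, and n, mean and SD by arm would let anyone compute a crude difference. What is missing is a prespecified between-arm estimate.
- A reader might take it as stated that the ZBI is collected in both arms. That is an inference from the objective. The questionnaire list under Intervention (LuCApp) omits the ZBI, the schedule under Standard of care concerns patients' own questionnaires, and the time-point figure is not available in the text reviewed.
- A reader might infer that randomisation alone makes the end-of-study contrast valid. Participants leave the study at treatment discontinuation, withdrawal, study termination or death, and 30% attrition is assumed, so respondents are a subset formed after randomisation. The ZBI also needs an available caregiver. The trial is unblinded, and the SCNS-SF34 is completed by app in one arm and on paper or by telephone in the other. A confidence interval covers sampling error, not these sources of bias.

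**Conclusion.** The mismatch is real and cheap to correct. Two comparative objectives have no prespecified between-arm estimate, and nothing elsewhere in the plan supplies one. The sample size and primary inference are untouched.

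The likely precision is modest: a half-width of 0.36 to 0.38 SD at 109 to 120 evaluable patients, and 0.45 SD at an assumed 80. The upper figure of 120 is optimistic, since it borrows the 12-week target for an end-of-study measure. The ZBI figures in points rest on an assumed SD of 12 to 16 and on collection in both arms. The estimate would be exploratory, among respondents, and could not by itself establish an effect on needs or burden.

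**What to change.** In Statistical methods:

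- Keep the graphical and numerical summary for usability.
- For the four SCNS-SF34 domain scores and the ZBI total at end of study, report the between-arm mean difference with 95% CI from a linear model with arm, centre and therapy (the stratification factors). Label it exploratory and make no significance claims.
- State that the ZBI is collected from caregivers in both arms.
- Report completion by arm, with counts of deaths, dropouts and patients without a caregiver.
- Note that the contrast is among respondents and is open to bias from missing data, unblinded reporting and, for the SCNS-SF34, different modes of completion.

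If the sponsor prefers description only, the alternative is to reword the two objectives in Outcomes as descriptive and say that the summaries will be by arm.

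The cost is a few lines of text, about five extra models and some added multiplicity. Provided that the ZBI is already planned in both arms, no new data are needed.
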